10.3.4. Analysis of safety and tolerability parameters

A) Data on AE/AR, Indicators of descriptive statistics (frequency and part in percent) and a list of adverse reactions according to the MeDRA classification

B) Data on SAE. Indicators of descriptive statistics (frequency and part in percent) and a list of adverse reactions according to the MeDRA classification.

Clinically significant deviations in indicators characterizing the safety and tolerability of the drug: Laboratory results of general blood analysis, biochemical blood analysis and general urinalysis; the result of determining the Coombs test and signs of hemolysis.

Provide descriptive statistics for these indicators (n, arithmetic mean, median, standard deviation, minimum and maximum value) for all visits.

To evaluate the dynamics of laboratory indicators, we used the Student's test for paired data or the Wilcoxon signed rank test, depending on the normality of the distribution of paired differences ["after" - "before"]. Create dichotomous variables with the categories "normal" and "abnormal", calculate the indicators of descriptive statistics (frequency and part in %) for these variables.

Measurement results of heart rate, blood pressure, respiratory rate, body temperature. Indicators of descriptive statistics (n, arithmetic mean, median, standard deviation, minimum and maximum value) for each visit in accordance with the patient examination scheme. Evaluate the trend of changing these parameters.

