The time of each blood draw and the start time of drug administration should be recorded; during each administration of the drug, it is necessary to evaluate the physical data, such as heart rate, blood pressure, body temperature, respiratory rate, and the severity of hemorrhagic syndrome. Patients' serum samples should be stored frozen at the temperature of -65 - -85 ° C (second aliquot) to ensure the possibility of performing repeat laboratory tests if necessary, in the future. The study involves scheduled visits of patients to the doctor:

1st visit (Day -14 – Day -1) – the patients are screened, checked for compliance with the criteria of inclusion / non-inclusion (exclusion), enrolled in the study;

2nd visit (Day 0 - Day +1 – Day +2) – hospitalization, administration of the study drug for 2 days, physical examination, assessment of the status of hemorrhagic syndrome, blood sampling to determine platelet count, manual platelet counts, Coombs test, Total IgG levels (g/l);

¹ Due to the variability in PLT levels in patients with chronic immune thrombocytopenia (wave-like), it is possible to re-screen or extend the duration of the screening stage, but only if the study subject meets all other specified inclusion criteria, does not have non-inclusion and exclusion criteria.

| Bioven | |
|----------------------------|--|
| Trial Code: 2021-BV-ITP-BP | |

3rd visit (Day $+7 \pm 1$ day) – physical examination, assessment of the status of hemorrhagic syndrome, blood sampling to determine platelet count, manual platelet counts, Coombs test in case hemolysis was detected during the previous visit (according to the laboratory data);

4th visit (Day $+14 \pm 2$ days) – physical examination, assessment of the status of the hemorrhagic syndrome, blood sampling to determine platelet count, manual platelet counts, Coombs test in case hemolysis was detected during the previous visit (according to the laboratory data).

If a decrease of platelets count $< 30 \times 10^9/L$ was recorded, then approximately a day after the visit, an additional blood test is performed with a platelet count.

This visit can be performed by telephone / video, provided that the patient's status can be adequately assessed and biomaterials for laboratory tests can be sampled in Local Laboratory or at the collection point of the or Central Laboratory designated by the Sponsor;

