5th visit (Day +21 \pm 3 days) – physical examination, assessment of the status of hemorrhagic syndrome, blood sampling to determine platelet count, manual platelet counts, biochemical blood test, Coombs test in case hemolysis was detected during the previous visit (according to the laboratory data).

If a decrease of platelets count $< 30 \times 10^9/L$ was recorded, then approximately a day after the visit, an additional blood test is performed with a platelet count.

This visit can be performed by telephone / video, provided that the patient's status can be adequately assessed and biomaterials for laboratory tests can be sampled in Local Laboratory or at the collection point of the Central Laboratory designated by the Sponsor;

6th visit (Day +28 + 1-3 days) – physical examination, assessment of the status of the hemorrhagic syndrome, blood sampling to determine platelet count, manual platelet counts, biochemical blood test, Coombs test, Total IgG levels (g/l).

If a decrease of platelets count $< 30 \times 10^9/L$ was recorded, then approximately a day after the visit, an additional blood test is performed with a platelet count.

This is a face-to-face visit. Completion of the study.

Statistical analysis:

Populations for statistical analysis:

ITT (Intention-to-treat population) – all participants of the study who have taken the study drug at least once. The data obtained from this sample will be used for safety analysis.

PP (Per Protocol) – all patients who have met the requirements of the protocol. This population includes all patients who received the protocol-prescribed therapy in full, who completed all the prescribed visits and did not have significant deviations from the protocol. The data obtained from this sample will be used for analysis based on efficacy criteria.

Sample size calculation.

Statistical analysis of endpoints will be descriptive with testing of the null hypothesis (non-inferiority study).

In accordance with the EU recommendations on the clinical investigation of human normal immunoglobulin for intravenous administration (*Guideline on the clinical investigation of human normal immunoglobulin for intravenous administration (IVIg), EMA/CHMP/BPWP/94033/2007 rev. 4, 16 Dec 2021*) the obtained results will be compared with literature data.

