6.2. Clinical stage

Visiting plan

The study involves scheduled visits of patients to the doctor:

1st visit (Day -14 - Day -1) - Screening, verification of compliance with the inclusion/exclusion criteria, enrollment in the study; due to the variability of PLT levels in patients with chronic immune thrombocytopenia (wave), it is possible to re-screen or extend the duration of the screening phase, but only if the subject meets all other specified inclusion criteria and has no inclusion or exclusion criteria;

2nd visit (Day 0 - Day +1 – Day +2) - hospitalization, administration of the study drug for 2 days, physical examination, assessment of the status of hemorrhagic syndrome, blood sampling to determine the platelet count by Fonio, Coombs test, determination of Ig G level (g/1);

3rd visit (Day +7 \pm 1 day) - physical examination, assessment of the status of hemorrhagic syndrome, blood sampling to determine platelet counting by the Fonio method, Coombs test in case hemolysis was detected during the previous visit (according to the laboratory data);

4th visit (Day +14 ± 2 day) -physical examination, assessment of the status of hemorrhagic syndrome, blood sampling to determine the level of platelets by Fonio; Coombs tests, in case of detection of hemolysis according to the laboratory examination at the previous visit, determination of the level of Ig G (g/l). If a decrease in platelet count < 30 x 109/L is detected, an additional blood test with Fonio platelet count is performed one day after the visit.

This visit can be performed by telephone/video, if it is possible to adequately assess the patient's status and take biomaterials for laboratory tests at the collection point of the Central Laboratory designated by the Sponsor;

5th visit (Day +21 \pm 3 day) – physical examination, assessment of the status of hemorrhagic syndrome, blood sampling to determine platelet counting by the Fonio method, biochemical blood test, Coombs test in case hemolysis was detected during the previous visit (according to the laboratory data).

This visit can be performed by telephone / video, provided that the patient's status can be adequately assessed and biomaterials for laboratory tests can be sampled at the collection point of the Central Laboratory designated by the Sponsor;

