6.3 Stage of follow-up and completion

The stage lasts from the last administration of the study drug and for 4 weeks.

The procedures are performed according to the schedule of procedures (Section 6.4, Table 1). If a decrease in platelet count $< 30 \times 109/L$ is detected, an additional blood test with platelet count by Fonio is performed one day after the visit.

Face-to-face or telephone/video visits are made to assess the patient's condition. The patient visits the blood collection point for laboratory testing. The investigator fills in all information about the patient's condition and examination results in the IRF.

| Bioven | |
|----------------------------|-------------|
| Trial Code: 2021-BV-ITP-BP | Version 1.2 |

6.4 Schedule of study procedures in tabular form Table 1. Schedule of study procedures.

| Visits | Visits 1 | Vi | sits 2 (госпіт | алізація) | Visits 3 | PLT control | Visits 4 | PLT control | Visits 5 | PLT control | Visits 6 | PLT contro |
|--|------------------------|-----------|----------------|-----------|-----------|----------------|-----------|----------------|-----------|----------------|-----------|---------------|
| Study stage | Screening ² | IMP admin | . IMP admin | Follow-up | Follow-up | every | Follow-up | every | Follow-up | every | Follow-up | every |
| Day relative to the first administration of the drug/Injection | Day (-14 -1) | Day 0 | Day +1 | Day +2 | Day +7 | day* | Day +14 | day* | Day +21 | day* | Day +28 | day* |
| Signing the Informed Consent Form | • | | | | | | | | | | | |
| Collection of demographics data | • | | | | | | | | | | | |
| Collection of anthropometric data, body weight ³ | • | • | • | | | | | | | | | |
| Collection of medical history ⁴ | • | | | | | | | | | | | |
| Objective physical examination 5 | • | • | • | • | • | | • | | • | | • | |
| Measurement of vital signs 6 | • | • | • | • | • | | • | | • | | • | |
| ECG in 12 leads; | • | | | | | | | | | | | |
| Coombs Direct Test (Antiglobulin Test)* | • | | | • | * | | * | | * | | • | |
| Determination of the level of total Ig G in the blood (g/l) | • | | | • | • | | • | | • | | • | |
| General blood test ⁷ | • | | | • | • | * | • | * | • | * | • | * |
| Biochemical blood test 8 | • | | | | | | | | | | • | |
| Blood test for blood group and Rh factor | • | | | | | | | | | | | |
| Coagulogram (PTI, APTT, fibrinogen) | • | | | | | | | | | | | |
| General urine analysis ⁹ | • | | | | | | | | | | | |

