All screening data are entered into the primary documentation and IRF of patients. The researcher checks the patient's compliance with the inclusion/exclusion (exclusion) criteria and decides on possible participation in the clinical trial. Due to the variability in PLT levels in patients with chronic immune thrombocytopenia (wave-like), it is possible to re-screen or extend the duration of the screening stage, but only if the study subject meets all other specified inclusion criteria, does not have non-inclusion and exclusion criteria.

Visit 2. (Day 0, Day +1, Day +2): Study Drug administration within 2 days. Observation.

Content of the visit:

The patient is hospitalized for 3 days for the introduction of the Study Drug (SD).

- 15 minutes before the start of each SD administration and after drug administration, a
 physical exploring is performed: determination of the dynamics of the hemorrhagic
 syndrome (exploring of the skin and mucous membranes, the presence / absence of
 bleeding); palpation and percussion of the abdominal organs; auscultation and percussion of
 the heart and lungs; Measurement of vital signs (body temperature, heart rate, blood pressure,
 respiratory rate);
- Administration of SD for 2 consecutive days at a dose of 0.8-1.0 g/kg per day (course dose 1.6-2.0 g/kg);
- After 48 hours (+/- 2 hours) from the beginning of the first SD administration, a blood sample is taken for general blood test, biochemical blood test, Coombs' test and Ig G level according to the "Schedule of Procedures";
- AE/AR registration;
- Discharge of the patient and appointment of the date of the next visit.

Visit 3 (Day +7 ± 1 day): Observations.

The patient is:

- Physical exploring is performed: determination of the dynamics of the hemorrhagic syndrome (exploring of the skin and mucous membranes, the presence / absence of bleeding); palpation and percussion of the abdominal organs; auscultation and percussion of the heart and lungs;
- Measurement of vital signs (body temperature, heart rate, blood pressure, respiratory rate);
- General blood test: hemoglobin, hematocrit, erythrocytes, leukocytes, platelet count according to Fonio;
- Coombs' test is performed in case of hemolysis according to the laboratory test at the previous visit;
- Determination of total IgG in serum (g/l);
- Rating according to the exclusion criteria;
- AE/AR registration;
- Discharge of the patient and appointment of the date of the next visit.

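### Post-dose biochemistry falls on different days in Table 1 of 6.4, in 6.6 and in the synopsis and 6.2, so the safety laboratory data depend on which section a site follows

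*Combined protocol and SAP*

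**What the plan says.** Biochemistry here means ALT, AST, bilirubin, creatinine, urea and glucose. Four places schedule it.

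- **Section 6.4, Table 1.** The row "Biochemical blood test 8" is marked at screening and Day 28, with nothing between.
- **Section 6.6, Visit 2.** At 48 hours "a blood sample is taken for general blood test, biochemical blood test, Coombs' test and Ig G level", with a reference to the schedule of procedures. Biochemistry is listed again at Visit 6, and not at Visits 3 to 5.
- **Synopsis.** Visit 2 lists "manual platelet counts, Coombs test, Total IgG levels (g/l") and no biochemistry. Visit 5 (Day 21) lists "manual platelet counts, biochemical blood test, Coombs test in case hemolysis was detected during the previous visit". Visit 6 has biochemistry.
- **Section 6.2.** Again none at Visit 2. Visit 5 lists "platelet counting by the Fonio method, biochemical blood test, Coombs test in case hemolysis was detected during the previous visit". The final visit, dated Day 30 ± 3 here, has biochemistry.

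The Coombs test is done for everyone at screening, 48 hours and the final visit. On Days 7, 14 and 21 it is conditional. In the words of 6.6, "Coombs' test is performed in case of hemolysis according to the laboratory test at the previous visit".

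For the analysis, 10.3.4 names as its indicators "Laboratory results of general blood analysis, biochemical blood analysis and general urinalysis; the result of determining the Coombs test and signs of hemolysis" and instructs: "Provide descriptive statistics for these indicators (n, arithmetic mean, median, standard deviation, minimum and maximum value) for all visits". Section 10.3.6 replaces missing data by LOCF, or by another method where carrying forward does not apply. It makes no exception for safety laboratory values.

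**The concern.** Section 9.1 makes two laboratory outcomes safety endpoints: the frequency of clinically significant laboratory changes after infusion, and the course of laboratory parameters over time. Both depend on which post-dose samples exist. Sites that each obey a different section would collect different data, and a sample that was not drawn cannot be recovered at analysis.

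The timing also matters clinically. Section 2.4 calls for serum creatinine monitoring in all patients given IgG, and a repeat course is allowed on Days 14 to 28. A site working from Table 1 has no scheduled post-dose creatinine or bilirubin until Day 28.

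The instruction in 10.3.4 to summarise at all visits does not help, because no section schedules biochemistry at every visit and the Day 7 to 21 Coombs tests are done only in selected patients. The vital-signs line in the same section refers to the patient examination scheme. The laboratory line does not.

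**Working it through.** **1. The schedules side by side (post-dose biochemistry).**

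| Source | 48 h | Day 7 | Day 14 | Day 21 | Final visit | Panels per patient |
|---|---|---|---|---|---|---|
| Table 1 (6.4) | no | no | no | no | Day 28 | 1 |
| 6.6 | yes | no | no | no | Day 28 | 2 |
| Synopsis | no | no | no | yes | Day 28 | 2 |
| 6.2 | no | no | no | yes | Day 30 ± 3 | 2 |

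Only the final visit is common to all. For the 40 patients planned, the totals are 1 × 40 = 40 panels under Table 1, 2 × 40 = 80 under 6.6, and 2 × 40 = 80 under the synopsis or 6.2.

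**2. Blood volumes in 6.5.10.** Listed units: general blood test 4 ml, biochemistry with IgG 10 ml, virology with antinuclear antibodies 5 ml, blood group 5 ml, Coombs 4 ml, coagulogram 4 ml.

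- Screening: 4 + 10 + 5 + 5 + 4 + 4 = 32 ml. Stated 32, so the units reproduce the plan's figure.
- Visit 2 under 6.6: 4 + 10 + 4 = 18 ml. Stated 13, short by 5.
- Visit 5 under the synopsis or 6.2: 4 + 10 = 14 ml. Stated 9, short by 5.
- Visit 6: 4 + 10 + 4 = 18 ml. Stated 23, over by 5.

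These sums take the 10 ml entry whole, because 6.5.10 gives no volume for biochemistry alone or IgG alone. If IgG alone takes 5 ml (an inference), the post-dose figures match Table 1: Visit 2 is 4 + 4 + 5 = 13, Visits 3 to 5 are 4 + 5 = 9, and Visit 6 is 4 + 10 + 4 + 5 = 23. That reading counts 10 + 5 ml for biochemistry and IgG at Visit 6, but only 10 ml for the same two tests at screening. No single rule reproduces every stated volume.

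Adding biochemistry at Visit 2 therefore costs between 18 − 13 = 5 ml (shared 10 ml sample) and (4 + 10 + 4 + 5) − 13 = 10 ml (separate IgG sample).

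**3. Last scheduled creatinine before a repeat course on Day 14 at the earliest.**

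- Table 1 site: the latest possible screening day is Day −1, so 14 − (−1) = 15 days or more. No firm upper limit exists, because screening may be extended.
- 6.6 site: 14 − 2 = 12 days for a course on Day 14, up to 28 − 2 = 26 days for one on Day 28.
- Synopsis or 6.2 site: as for Table 1 until the Day 21 visit, and the Day 21 value after it.

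**The case against.** The best defence is that Table 1 governs: the 48-hour text in 6.6 and the laboratory text in 6.5.6 both point to the schedule of procedures. But no precedence rule is written, and the 48-hour text asks for a test that Table 1 does not mark. Even if Table 1 does govern, the other three places need correcting. Footnote 8 on its biochemistry row is unreadable in this copy and might add days. Section 6.6 and the synopsis and 6.2 contradict each other without it.

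Several stronger conclusions are tempting and are not supported.

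- **Hemolysis would go unseen without bilirubin.** The trigger for the conditional Coombs test is laboratory data in general. A blood count is scheduled at every post-dose visit, with hemoglobin, hematocrit and erythrocytes listed at Visits 3 to 6. Everyone has a Coombs test at 48 hours, and 2.4 requires laboratory analysis if symptoms of hemolysis appear.
- **A repeat course could be given with no renal check.** Sections 6.2 and 7.4 require control of kidney function at administration, 6.5.10 permits extra biochemistry, and 6.6.1 permits unscheduled tests. What stands is that no creatinine day is fixed for it.
- **The volumes rule out an extra panel, or prove that Table 1 was intended.** Section 6.5.10 allows one additional sample of 20 ml, which would cover the shortfall. The match to Table 1 rests on an inferred volume.
- **LOCF would dilute the 48-hour change.** A value never scheduled is not naturally missing, 10.3.6 offers an alternative method, and nothing says how many sites would follow each section.
- **The Day 7 to 21 Coombs percentages would mislead by a known amount.** Section 10.3.4 asks for n, its all-visits wording is not attached to the normal/abnormal percentages, and the documents give no expected counts.

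**Conclusion.** The contradiction is real and should be corrected. There are three incompatible schedules for post-dose biochemistry, with one common time point, 40 against 80 planned panels, and two visit volumes that are each 5 ml short if the listed 10 ml sample is drawn. The consequence is safety laboratory data that are not comparable between sites and, under Table 1, no scheduled creatinine or bilirubin between screening and Day 28.

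The effect is confined to the description of safety. The screening-to-final comparison survives under every section, and the primary endpoint and sample size are untouched. The conclusion assumes that the unreadable Table 1 footnotes do not add biochemistry days. If they do, the Table 1 figures change, but the conflict between 6.6 and the synopsis and 6.2 remains. Any numerical bias from LOCF or from selective Coombs testing would have to be assumed, so none is claimed.

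**What to change.** 1. Make Table 1, the synopsis, 6.2 and 6.6 agree on biochemistry at 48 hours and at Day 28 for all patients. Keep Day 21 only if the sponsor intends it. Use one date for the final visit.
2. In 6.5.10, raise the Visit 2 volume from 13 ml to at least 18 ml. If Day 21 is kept, raise Visit 5 from 9 ml to at least 14 ml.
3. In 10.3.4, write: *Laboratory results are summarised at the visits where the test is scheduled for every patient. Coombs results are given as number and percent at screening, 48 hours and Day 28. Results from Days 7, 14 and 21 are listed with the number of patients tested.*
4. In 10.3.6, write: *LOCF is not applied to safety laboratory values. The number observed is shown at each visit.*

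The cost is wording in six places and up to about 40 extra panels at 48 hours, if sites would otherwise have followed Table 1. They come from a draw already scheduled, with 5 to 10 ml more blood per patient and no added visit or venepuncture.

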10.3.5. Significance level

The level of significance for the Shapiro-Wilk test is set at 0.01, and for other statistical tests at 0.05. In the case of the effect of multiple comparisons, the adjustment of the level of significance will be applied using the Holm method or the Benjamini-Hochberg method.

10.3.6. Work with missing or incomplete data.

Missing or incomplete data will be replaced using the Last-Observation-Carried-Forward (LOCF) method. Or by the method of enlarging the intervals for series where the transfer of the last measurement is not applicable.

